1. PROTOCOL SUMMARY

Protocol Title:

An Open-Label, Multicenter, Rollover Study to Provide Continued Treatment for Participants With Advanced Malignancies Previously Enrolled in Studies of Pemigatinib

Protocol Number: INCB 54828-801

Objectives and Endpoints:

[Table 1](#) presents the primary and major/key secondary objectives and endpoints.

Table 1: Objectives and Endpoints

Objectives	Endpoints
To evaluate the long-term safety and tolerability of pemigatinib.	Frequency and nature of AEs and SAEs as assessed by CTCAE v5.0.

Overall Design:

[Table 2](#) presents the key study design elements. Further study details are presented after the table.

Table 2: Key Study Design Elements

Study Phase	Phase 2
Clinical Indication	Treatment of patients with advanced malignancies
Population	Male and female participants at least 18 years of age who are actively receiving treatment with pemigatinib under a parent protocol and receiving clinical benefit and who do not have access to pemigatinib outside of a clinical trial.
Number of Participants	Approximately 20 participants will be enrolled from prior pemigatinib studies.
Study Design	Single-arm, open-label, rollover
Estimated Duration of Study Participation	Participants will be allowed to continue to receive pemigatinib until they meet the criteria noted in Section 7.1 .
Data Safety Monitoring Board/Data Monitoring Committee	No
Coordinating Principal Investigator	Not applicable

[Figure 1](#) presents the study design schema, and [Table 3](#) presents the schedule of activities.

Figure 1: Study Design Schema

[figure not shown]

Table 3: Schedule of Activities

	Day 1 of Each Cycle	EOT	Safety Follow-Up	Comments
Informed consent	X*			*Only on Day 1 of rollover protocol.
Demography	X*			*Only on Day 1 of rollover protocol.
Contact IRT	X	X		
Dispense pemigatinib	X			
Collect remaining pemigatinib	X*	X		*Starting Cycle 2 Day 1.
Administer pembrolizumab (only for participants receiving under parent protocol)	X*			*Administer 200 mg IV once every 3 weeks on Day 1 of a 21-day cycle (3 weeks).
Administer INCMGA00012 (only for participants receiving under parent protocol)	X*			*Administer 500 mg IV once every 4 weeks on Day 1 of a 28-day cycle (4 weeks).
AE assessments	X	X	X	
12-lead ECG	X*	X		*Every 6 cycles starting from last ECG on parent study.
Ophthalmologic examinations	X*			*Every 3 cycles starting from last eye examination on parent study.
Serum chemistry	X	X		

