2.3. Benefit/Risk Assessment

More detailed information about the known and expected benefits and risks and reasonably expected AEs of pemigatinib, INCMGA00012, and pembrolizumab may be found in the [pemigatinib IB](#), [INCMGA00012 IB](#), and [KEYTRUDA® \(pembrolizumab\) prescribing information](#), respectively.

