5.1. Inclusion Criteria

Participants are eligible to be included in the study only if all of the following criteria apply:

1. Currently enrolled and receiving treatment in an Incyte-sponsored clinical study (parent protocol) of pemigatinib as monotherapy or combination therapy.
2. Currently benefiting from and tolerating treatment with pemigatinib, as determined by the investigator.
3. Demonstrated compliance, as assessed by the investigator, with the parent protocol requirements.
4. Willingness and ability to comply with scheduled visits, treatment plans, and any other study procedures.
5. Currently have no evidence of progressive disease, as determined by the investigator, following treatment with pemigatinib as monotherapy or combination therapy.
6. Willingness to avoid pregnancy or fathering children based on the criteria below.
 - a. Male participants must agree to take appropriate precautions to avoid fathering children (with at least 99% certainty) from signing of the ICF through 90 days after the last dose of pemigatinib and 6 months after the last dose of gemcitabine and/or cisplatin and must refrain from donating sperm during this period. Permitted methods that are at least 99% effective in preventing pregnancy (see [Appendix A](#)) should be communicated to the participants and their understanding confirmed. NOTE: Men being treated with gemcitabine must be advised to seek further advice regarding cryoconservation of sperm before treatment because of the possibility of infertility due to therapy with gemcitabine.
 - b. Women of nonchildbearing potential (ie, surgically sterile with a hysterectomy and/or bilateral oophorectomy OR ≥ 12 months of amenorrhea) are eligible.
 - c. Women of childbearing potential must have a negative serum pregnancy test at signing of the ICF and before the first dose on Day 1 and must agree to take appropriate precautions to avoid pregnancy (with at least 99% certainty) from signing of the ICF through safety follow-up (30-35 days after the last dose of pemigatinib) and through 6 months after the last dose of gemcitabine and/or cisplatin. Permitted methods that are at least 99% effective in preventing pregnancy (see [Appendix A](#)) should be communicated to the participants and their understanding confirmed.
7. Written informed consent obtained prior to enrolling in the rollover study. If consent cannot be expressed in writing, it must be formally documented and witnessed, ideally via an independent trusted witness.

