6. STUDY TREATMENT

6.1. Study Treatments Administered

[Table 5](#) presents the study treatment information. This information is also found in the parent protocol.

Table 5: Study Treatment Information

	Study Treatment 1	Study Treatment 2	Study Treatment 3
Study treatment name:	Pemigatinib (INCB054828)	INCMGA00012 (INCB 54828-101 only)	Pembrolizumab (INCB 54828-101 only)
Dosage formulation:	Oral	IV	IV
Unit dose strength(s) /dosage level(s):	2 mg, 4.5 mg, 9 mg, 13.5 mg	500 mg/500 mg	200 mg
Administration instructions:	Taken by mouth once daily	Administered over 60 minutes once every 4 weeks (Day 1 of a 28-day cycle)	
Packaging and labeling:	Pemigatinib 4.5 mg, 9 mg, and 13.5 mg tablets will be provided in 14-count bottles; 2 mg tablets will be provided in 60-count bottles. Each bottle will be labeled as required per country requirement.	500 mg vials Each vial will be labeled as per country requirement.	Commercially labeled product
Storage:	Room temperature	Stored upright under refrigeration at 2°C to 8°C (36°F-46°F) and protected from light	Stored under refrigeration at 2°C to 8°C (36°F-46°F)
Status of treatment in participating countries:	Approved	Not approved	Approved

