The following methods during the Protocol-defined timeframe in Section 5.1 that can achieve a failure rate of less than 1% per year when used consistently and correctly are considered as highly effective birth control methods:

- Combined (estrogen and progestogen containing) hormonal contraception associated with inhibition of ovulation^d
 - oral
 - intravaginal
 - transdermal
- Progestogen-only hormonal contraception associated with inhibition of ovulation^d
 - oral
 - injectable
 - implantable^e
- Intrauterine device^e
- Intrauterine hormone-releasing system^e
- Bilateral tubal occlusion^e
- Vasectomized partner^{e,f}
- Sexual abstinence^c

FSH = follicle-stimulating hormone; HRT = hormone replacement therapy.

^a Documentation can come from the site personnel's review of the participant's medical records, medical examination, or medical history interview.

^b If the male participant has a partner with childbearing potential, the partner should also use contraceptives.

^c In the context of this guidance, sexual abstinence is considered a highly effective method only if defined as refraining from heterosexual intercourse during the entire period of risk associated with the study treatments. The reliability of sexual abstinence needs to be evaluated in relation to the duration of the clinical study and the preferred and usual lifestyle of the participant.

^d Hormonal contraception may be susceptible to interaction with the investigational medicinal product, which may reduce the efficacy of the contraception method. In this case, 2 methods of contraception should be used.

^e Contraception methods that in the context of this guidance are considered to have low user dependency.

^f Vasectomized partner is a highly effective method of avoiding pregnancy provided that partner is the sole sexual partner of the WOCBP study participant and that the vasectomized partner has received medical assessment of the surgical success.

Source: [Clinical Trials Facilitation and Coordination Group 2020](#).

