3. STUDY DESIGN

This rollover study allows participants from multiple Protocols, who are receiving clinical benefit from pemigatinib as either monotherapy or combination therapy, to continue to be treated following the completion of the parent study (also referred to as parent Protocol). The population for the rollover study should be consistent with the population defined in each parent Protocol. The primary eligibility criterion for a participant to enter the rollover study is participation in an Incyte-sponsored study (parent Protocol) and receiving ongoing study treatment.

[figure not shown]
Participants who have enrolled in a prior study (parent Protocol) with pemigatinib as monotherapy or combination therapy and are assessed by the investigator to continue to benefit from ongoing treatment and who cannot access pemigatinib outside of a clinical trial will be eligible.

Disease assessments will be performed per standard of care, with date of progression reported and safety data collected.

Once a participant has rolled over into this study from a parent study, the database for the parent study will be closed and locked, and the parent Protocol study will be considered completed and closed; however, the participant in the rollover study will still be treated as per the plan outlined in the parent Protocol. The parent Protocols include INCB 54828-101 (FIGHT-101); INCB 54828-201 (FIGHT-201); INCB 54828-202 (FIGHT-202); and INCB 54828-207 (FIGHT-207). The study treatments include pemigatinib, INCMGA00012 (INCB 54828-101 only), and pembrolizumab (INCB 54828-101 only).

The study begins when the first participant signs the study informed consent form. The end of the study is defined as the date of the last visit of the last participant in the study. It is estimated that an individual will participate for approximately 12 months. The study is considered completed when the last participant's last visit has occurred. [Figure 1](#) elaborates on the study design.

Figure 1: Study Design Schema

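### Criteria 6c and 6a set contraception periods for gemcitabine/cisplatin, which are not study treatments here, and none for pembrolizumab or INCMGA00012, which are

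*Protocol*

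**What the plan says.** Criterion 6c in Protocol Section 5.1 starts contraception at consent and continues it through "safety follow-up (30-35 days after the last dose of pemigatinib) and through 6 months after the last dose of gemcitabine and/or cisplatin". Criterion 6a, for men, gives 90 days after pemigatinib and the same 6 months after gemcitabine and/or cisplatin. It adds a note on sperm preservation for men treated with gemcitabine. Neither criterion names an antibody.

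Appendix A sets no period of its own. For women of childbearing potential it refers back to Section 5.1: "The following methods during the Protocol-defined timeframe in Section 5.1 that can achieve a failure rate". Its footnote c, on abstinence, speaks of refraining "during the entire period of risk associated with the study treatments", and the abbreviations list defines study treatment to include combinations.

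SAP Section 3 states: "The study treatments include pemigatinib, INCMGA00012 (INCB 54828-101 only), and pembrolizumab (INCB 54828-101 only". Protocol Table 5 lists the same three drugs. Table 3 schedules pembrolizumab on Day 1 of a 21-day cycle and INCMGA00012 on Day 1 of a 28-day cycle, each only for participants already receiving it under the parent protocol. Gemcitabine and cisplatin are named nowhere in the two documents except in criterion 6.

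Two other provisions bear on the point. Section 5 and exclusion 3 keep the parent protocol's eligibility criteria in force. Exclusion 4 bars participants who expect to conceive or father children up to the end of safety follow-up or up to 90 days after the last study treatment. It does not say which of the two dates applies to whom.

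**The concern.** A contraception rule should follow the drugs the participant receives. This one names two drugs that the study does not give and omits two that it does. Because Appendix A makes Section 5.1 the reference for timing, a site reading this protocol alone would advise a woman on a combination by the date of her last pemigatinib dose. It would not consider when the antibody was last infused.

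What is at stake is possible fetal exposure to an antibody after the stated period has ended. This is a participant-safety and drafting matter. It does not touch adverse event reporting, the counts of treatment-emergent events, or any planned summary.

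**Working it through.** The plan states no figure for an antibody period, so there is none to reproduce. The check sets the drug lists side by side and then works out what 6c implies.

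**Drug lists**

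| Drug | Study treatment here? (Tables 3 and 5; SAP 3) | Period after last dose in 6c | Period in 6a |
|---|---|---|---|
| Pemigatinib | Yes | 30-35 days | 90 days |
| Pembrolizumab | Yes, from INCB 54828-101 | None | None |
| INCMGA00012 | Yes, from INCB 54828-101 | None | None |
| Gemcitabine/cisplatin | No | 6 months | 6 months |

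**Time from last infusion to the end of 6c**

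Inputs: infusion on Day 1 of a 21-day or 28-day cycle (Table 3), and 30-35 days after the last pemigatinib dose (6c). Assumption: the last pemigatinib dose falls on Day d of the last infused cycle.

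- Gap from infusion to last pemigatinib dose = d − 1, which is 0-20 days (21-day cycle) or 0-27 days (28-day cycle).
- Cover after the last infusion = (30 to 35) + gap.
- Pembrolizumab: 30 + 0 = 30 to 35 + 20 = 55 days, or 30/21 = 1.4 to 55/21 = 2.6 dosing intervals.
- INCMGA00012: 30 + 0 = 30 to 35 + 27 = 62 days, or 30/28 = 1.1 to 62/28 = 2.2 dosing intervals.

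**Is that long enough?**

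Let T be the antibody risk period in days after the last infusion. T is not in the documents, so the values below are assumptions. Shortfall = max(0, T − cover).

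| Assumed T (days) | Pembrolizumab | INCMGA00012 |
|---|---|---|
| 30 | none | none |
| 60 | 5-30 days | 0-30 days |
| 90 | 35-60 days | 28-60 days |
| 120 | 65-90 days | 58-90 days |

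Every entry holds only if pemigatinib stops within the last infused cycle. If the antibody stops earlier and pemigatinib continues, cover lengthens by that time and could exceed any T.

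**Exclusion 4**

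If its 90-day date applies to women and pemigatinib is the last drug taken, 6c ends 90 − 35 = 55 to 90 − 30 = 60 days before it.

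**The case against.** The strongest reply is that the antibodies are given only to participants from INCB 54828-101, and that protocol's criteria still bind. Section 5 and exclusion 3 say so, and Section 4.1 keeps the parent treatment plan. If INCB 54828-101 sets an antibody period, there may be no gap in practice. This stands as a limit on the consequence. The parent text is not among the documents, so the gap can be neither confirmed nor ruled out. It does not repair 6c, and a longer parent period would leave sites with two end dates and no rule on which governs.

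A second reply is that other text links the combination to avoiding conception. Exclusion 4 runs from the last study treatment, and Appendix A footnote c refers to the risk period of the study treatments. Section 2.3 points to the INCMGA00012 IB and the pembrolizumab prescribing information. It would therefore be wrong to infer that nothing in the protocol makes the link. But exclusion 4 is an eligibility rule with two alternative end dates, footnote c only defines when abstinence counts as a method, and 6c does not refer to the sources in Section 2.3.

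A third reply is that the gemcitabine/cisplatin wording covers exposure in a parent study. That is possible, but the documents do not say so. The note in 6a, which addresses men being treated with gemcitabine and advises action before treatment, reads as current or coming therapy. In any case the wording places no burden on anyone not exposed to those drugs.

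Lastly, reach is small. Enrolment is about 20 across all regimens. SAP Section 5.2 plans one combination column, pemigatinib 9 mg with pembrolizumab, and none for INCMGA00012. The number of women of childbearing potential on a combination is not given and could be zero. This stands.

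**Conclusion.** The point holds as a modest safety clarification. 6c and 6a carry a drug list that does not match this study's treatments. For women on a combination, 6c taken alone ends contraception 30-55 days after the last pembrolizumab infusion or 30-62 days after the last INCMGA00012 infusion. Those figures assume that pemigatinib stops within the last infused cycle and that the last infusion is on or before the last pemigatinib dose.

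A reader might infer three stronger things, none of which the documents support:

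- **That women are shown to be under-protected.** The result runs from no shortfall to several months depending on an assumed T, and the 6 months set for chemotherapy says nothing about antibody risk.
- **That time on contraception depends only on when pemigatinib stopped.** Parent criteria also apply and may require longer.
- **That a later pregnancy would go unnoticed.** Section 8.3.2.1 also allows tests when medically indicated or required by a country.

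The change is worth making at the next amendment.

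**What to change.** In 6c, replace the gemcitabine/cisplatin wording with: *and, for participants receiving pembrolizumab or INCMGA00012, through the period after the last infusion given in the current prescribing information or IB, or the parent protocol if longer*. The sponsor supplies the figure from those sources. Keep the chemotherapy wording only for a participant whose last dose under a parent protocol was within 6 months.

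Review the drug list in 6a in the same way, including the gemcitabine note. State in exclusion 4 which end date applies to women. Update the consent form to match.

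The cost is an amendment to two criteria and one exclusion plus a consent update. Section 8.1.1 already requires participants to consent to the current version. No visit or test is added. The downside is longer contraception for some combination participants, by an amount that depends on the period the sponsor states.

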
5.2. Exclusion Criteria

Participants are excluded from the study if any of the following criteria apply:

1. Able to access pemigatinib commercially or outside of a clinical trial.
2. Permanently discontinued from the parent protocol for any reason.
3. No longer meet the inclusion/exclusion criteria from the parent protocol if still receiving treatment.
4. Women who are pregnant or breastfeeding or participants expecting to conceive or father children within the projected duration of the study, starting with Day 1 of the rollover study visit through completion of safety follow-up or through 90 days from the date of last dose of study treatment.

5.3. Lifestyle Considerations

No restrictions are required.

5.4. Screen Failures

There are no screen failures for this rollover study. Only participants actively receiving treatment in another pemigatinib study (parent protocol) are eligible to enroll.

5.5. Replacement of Participants

Not applicable.

6. STUDY TREATMENT

6.1. Study Treatments Administered

[Table 5](#) presents the study treatment information. This information is also found in the parent protocol.

Table 5: Study Treatment Information

	Study Treatment 1	Study Treatment 2	Study Treatment 3
Study treatment name:	Pemigatinib (INCB054828)	INCMGA00012 (INCB 54828-101 only)	Pembrolizumab (INCB 54828-101 only)
Dosage formulation:	Oral	IV	IV
Unit dose strength(s) /dosage level(s):	2 mg, 4.5 mg, 9 mg, 13.5 mg	500 mg/500 mg	200 mg
Administration instructions:	Taken by mouth once daily	Administered over 60 minutes once every 4 weeks (Day 1 of a 28-day cycle)	
Packaging and labeling:	Pemigatinib 4.5 mg, 9 mg, and 13.5 mg tablets will be provided in 14-count bottles; 2 mg tablets will be provided in 60-count bottles. Each bottle will be labeled as required per country requirement.	500 mg vials Each vial will be labeled as per country requirement.	Commercially labeled product
Storage:	Room temperature	Stored upright under refrigeration at 2°C to 8°C (36°F-46°F) and protected from light	Stored under refrigeration at 2°C to 8°C (36°F-46°F)
Status of treatment in participating countries:	Approved	Not approved	Approved

6.2. Preparation, Handling, and Accountability

The investigator or designee must confirm appropriate temperature conditions have been maintained during transit for all study treatments received and any discrepancies are reported and resolved before use of the study treatment.

Only participants enrolled in the study may receive study treatment, and only authorized site staff may supply or administer study treatment. All study treatment must be stored in a secure, environmentally controlled, and monitored (manual or automated) area in accordance with the labeled storage conditions with access limited to the investigator and authorized site staff.

The investigator (or designee) is responsible for study treatment accountability, reconciliation, and record maintenance (ie, receipt, reconciliation, and final disposition records). Inventory and accountability records must be maintained and readily available for inspection by the study monitor and are open to inspection at any time by any applicable regulatory authorities. The investigator or designee must maintain records that document the following:

- Delivery of study drugs (except pembrolizumab for INCB 54828-101 only) to the study site.
- Inventory of study drugs at the site.
- Participant use of the study drugs, including tablets and/or vials from each supply dispensed.
- Return of study drugs (except pembrolizumab for INCB 54828-101 only) to the investigator or designee by participants.

The investigational product must be used only in accordance with the parent protocol and this protocol. The investigator will also maintain records adequately documenting that the participants were provided the specified study drug. These records should include dates, quantities, and any available batch or serial numbers or unique code numbers assigned to the investigational product and study participants.

Completed accountability records will be archived by the site. The investigator or designee will be expected to collect and retain all used, unused, and partially used containers of study drug until verified by the study monitor (unless otherwise agreed to by the sponsor). At the conclusion of the study, the investigator or designee will oversee shipment of any remaining study drug back to the sponsor or its designee for destruction according to institutional SOPs. If local procedures mandate on-site destruction of the investigational supply, the site should (where local procedures allow) maintain the investigational supply until the study monitor inspects the accountability records in order to evaluate compliance and accuracy of accountability by the investigative site. At sites where the study drug is destroyed before monitor inspection, the monitors rely on documentation of destruction per the site SOP.

Further guidance and information for the final disposition of unused study treatments are provided in the Pharmacy Manual from the parent protocol.

6.3. Measures to Minimize Bias: Randomization and Blinding

Not applicable.

